17.4.2 Supportive secondary safety endpoints (cohort I)

The following endpoints will be used to support the secondary objectives of evaluation of safety for up to 364 weeks of treatment:

- Incidence of adverse events, including injection site reactions
- Occurrence of anti-NNC0195-0092 and anti-hGH antibodies

Adverse events will be analysed using descriptive statistics. All adverse events with onset after the first administration of trial product and up until week 26 or 14 days after last trial drug administration, whichever comes first, will be included in the main trial period analysis. The adverse events will be summarised by treatment, MedDRA (Medical Dictionary for Regulatory Activities) system organ class and MedDRA preferred term. The descriptive statistics will include the number and percentage of subjects who experienced adverse events, the number of events and rate. Adverse events will be listed by treatment and subject with information on severity, relationship to trial product and demographics. Similar tables will be done for adverse events with onset after the first administration of trial product and up until week 52 for the extension trial period and for adverse events with onset after the first administration of trial product and up until week 104 and 156 , respectively, for the safety extension, and for adverse events with onset after the first administration of trial product and up until week 260 and 364 for the long-term safety extension trial period and follow-up period analysis.

Adverse events with onset 14 days or more after last trial drug administration will be reported in a separate listing. Adverse events with onset before first dosing will be reported in a separate listing.

All other safety endpoints will be analysed using descriptive statistics.

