5.2 Rationale for trial design

The trial is double-blinded with regards to different dose levels of once-weekly NNC0195-0092, but open labelled with regards to daily hGH as active-controlled arm. The open-label design is chosen in order to be able to compare local tolerability, (i.e. daily vs. weekly injections), which is not possible if a double-dummy design was applied. Furthermore, double-dummy design will not allow comparing patient satisfaction related to daily vs. weekly injections.

The safety extension trial period will be open labelled since only one dose level of NNC0195-0092 will be used. Additionally, in the long-term safety extension trial period, all subjects randomised to Norditropin® FlexPro® will be switched to NNC0195-0092 ([REDACTED] mg/kg/week). All subjects in cohort II and III will receive treatment with NNC0195-0092 ([REDACTED] mg/kg/week).

The trial will be observer blinded (applicable for cohort I only) with regards to primary endpoint (i.e. the person performing the height measurements will be blinded to treatment allocation). Observer blinding with regards to primary endpoint is not applicable for the long-term safety extension and any visits thereafter. GH treatment-naïve GHD pre-pubertal children is the trial target population for treatment as this is a sensitive and well-known model. The children need to be pre-pubertal to avoid interference of the pubertal growth spurt with the treatment effect. The trial will be multinational to ensure that the results are applicable for subjects with different demographic characteristics. Two additional age groups; cohort II (< 2 years and 26 weeks at screening) and cohort III (> 9 years (girls)/>10 years (boys) and ≤ 17 years at screening) are included in the long-

term safety extension trial period, based on a request from the FDA, as they may benefit from GH therapy.

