- Subjects randomised to Norditropin® FlexPro® should inject s.c. daily in the evening (to reflect standard treatment practice) throughout the trial. Injections with Norditropin® FlexPro® the night before blood sampling for anti-hGH antibodies must occur at least 12 hours prior to planned blood sampling.
- If a subject randomised to Norditropin® FlexPro® forgets or is unable to inject the dose in the evening, the dose should be skipped. The subject should continue on the next evening with the next scheduled dose.

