5.5 Rationale for treatment

All doses will be administered s.c. because this is the approved route of administration of Norditropin® and the intended route of administration of NNC0195-0092 when marketed.

The dosing regimen is once-weekly for NNC0195-0092 as the compound is developed as a once-weekly therapy for children and adults with GHD to provide improved convenience/compliance over standard hGH administration, which must be dosed daily. A trial in healthy subjects (NN8640-3915) and a trial in adults with GHD (NN8640-3947) showed that increased IGF-I levels from baseline were maintained for at least one week after dosing. Norditropin® FlexPro® will be administered in the evening, following GH standard treatment practice [18](#).

The dose selection for NN8640-4172 is to use the totality of evidence including data from NN8640-4042 as well as modelling and simulation of IGF-I profile to select dose levels. The proposed NNC0195-0092 dose levels, [REDACTED] mg/kg/week, [REDACTED] mg/kg/week and [REDACTED] mg/kg/week, were selected as follows:

- [REDACTED] mg/kg/week. At this dose level the maximum IGF-I level for NNC0195-0092 is expected to match the average IGF-I level of [REDACTED] mg/kg/day Norditropin®.
- [REDACTED] mg/kg/week. At this dose level the average weekly IGF-I level for NNC0195-0092 is expected to match the average IGF-I level of [REDACTED] mg/kg/day Norditropin®.
- [REDACTED] mg/kg/week. At this dose level the average weekly IGF-I level for NNC0195-0092 is expected to exceed the average IGF-I level of [REDACTED] mg/kg/day Norditropin® but remain below 2 SDS.

The dose selection for the safety extension periods in the trial

NNC0195-0092 ([REDACTED] mg/kg/week) has been chosen for the safety extension trial period as this dose would provide the highest exposure safety wise of the three doses investigated in the first year of the trial and will most likely be the dose with the lowest risk of potential being inferior efficacy wise to daily hGH.

The daily Norditropin® FlexPro® arm continues in the 2 year safety extension trial period making it possible to compare safety and efficacy to once-weekly NNC0195-0092.

NNC0195-0092 ([REDACTED] mg/kg/week) has been chosen for all subjects for the long-term safety extension trial period to collect long-term safety data.

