8.8.2 Diaries

At visit 2 the subjects will be provided with a diary device for electronic recording of data. The site staff will train the subject in the use of the diary device according to provided instructions.

The following information will be recorded in the diary.

- date, time and dose of injections of trial drug including any missed doses

Reminders will be available in the e-diary to remind the subject to record any medical problems and changes in medications and to discuss them with the investigator during site visits.

The investigator will assess whether the medical problem is to be considered an AE. If the medical problem is considered an AE, data should be recorded in the subject's medical records and reported in the eCRF according to section [12.2](#). The investigator or delegated staff must report changes in concomitant medication changes into the subject's medical records and into the eCRF.

Review of diaries must be documented in the subject's medical records. If clarifications of entries are needed or discrepancies in the diary are discovered, the parent or LAR must be questioned, and a conclusion must be made in the subject's medical record. Care must be taken not to bias the subject.

The e-diary device will be returned by the subject at the end of treatment visit.

The overall process for handling diaries is described in a manual.

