17.2 Definition of analysis sets

Three analysis sets are defined.

The Full analysis set (FAS) is defined as all randomised subjects that received at least one dose of randomised treatment. Only in exceptional cases may subjects be excluded from the FAS. Subjects will be analysed “as treated”.

The Safety analysis set (SAS) is defined as all randomised subjects that received at least one dose of randomised treatment. Subjects will be analysed “as treated”.

The Per Protocol (PP) analysis set is defined as subjects from the FAS who have not violated any inclusion/exclusion criteria and have used the randomised treatment for at least 22 weeks (for subjects receiving NNC0195-0092) or 154 days (for subjects receiving Norditropin® FlexPro®) during the main trial period. Subjects will be analysed “as treated”.

The subjects or observations to be excluded, and the reasons for their exclusion must be documented and signed by those responsible before the first pDBL. The subjects and observations excluded from analysis sets, and the reason for this, will be described in the CTR.

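### Section 17.4.2 summarises injection-site reactions per child, as counts and as an undefined rate, but not per injection, although the daily arm is scheduled for seven times as many injections as each weekly arm up to week 156

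*Combined protocol and SAP*

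**What the plan says.** The supportive safety endpoint in section 17.4.2 is "Incidence of adverse events, including injection site reactions". For the main period it covers events with onset after first dosing and "up until week 26 or 14 days after last trial drug administration, whichever comes first", with similar cumulative tables up to weeks 52, 104, 156, 260 and 364. The statistics are set for all adverse events together: "The descriptive statistics will include the number and percentage of subjects who experienced adverse events, the number of events and rate". Results are given by treatment, with listings that add severity and relationship to trial product. Section 17.4.3 mentions injection-site reactions again, under descriptive statistics only. Neither section defines the denominator of the rate or plans a summary per injection or per dose.

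The regimens differ in frequency. Section 5.5 states: "The dosing regimen is once-weekly for NNC0195-0092". Section 5.3 states: "Subjects randomised to Norditropin® FlexPro® should inject s.c. daily in the evening". Section 5.1 keeps the comparator arm on daily treatment until week 156, when it switches to weekly.

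Section 5.2 explains the unblinded comparator: "The open-label design is chosen in order to be able to compare local tolerability, (i.e. daily vs. weekly injections". Section 8.8.2 has the e-diary record "date, time and dose of injections of trial drug including any missed doses", so injections given can be counted.

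**The concern.** A percentage of children affected, or a rate per unit of time, is the product of two things: how often an injection causes a reaction, and how many injections are given. When the second differs sevenfold between arms, neither figure isolates the first. Two arms with the same table entries could differ about sevenfold per injection. A weekly product with a higher reaction frequency per injection could still show fewer affected children and fewer events than the daily comparator.

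The trial left the comparator unblinded partly to obtain a local-tolerability comparison, and section 3.2 says its results will inform dose selection for phase 3. A reader of the safety tables should be able to see which question each figure answers.

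**Working it through.** **Inputs from the documents.** Weekly dosing (5.5); daily dosing (5.3); a 26-week main period; about 45 children on the three weekly arms together and about 15 on the daily arm, allocated 1:1:1:1 (5.3); two injections per weekly dose above 50 kg (5.3).

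**Input not in the documents.** The reaction risk per injection. No expected count, percentage or rate of injection-site reactions is given, so there is no planned figure to reproduce. Risks of 0.1% to 1% are assumed below.

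**Step 1, the ratio.** Over 26 weeks: weekly 26 × 1 = 26 injections per child; daily 26 × 7 = 182; ratio 182 / 26 = 7. The per-protocol rule in section 17.2 embodies the same ratio, requiring that children "have used the randomised treatment for at least 22 weeks (for subjects receiving NNC0195-0092) or 154 days": 154 / 22 = 7.

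**Step 2, equal counts.** Scheduled injections per 15-child arm: weekly 15 × 26 = 390; daily 15 × 182 = 2,730. Exposure is 15 × 0.5 = 7.5 patient-years in each. Suppose five reactions in each arm:

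| | Weekly arm | Daily arm |
|---|---|---|
| Events per patient-year | 5 / 7.5 = 0.67 | 5 / 7.5 = 0.67 |
| Events per 1,000 injections | 5 / 390 × 1,000 = 12.8 | 5 / 2,730 × 1,000 = 1.8 |

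The time-based rates agree and the per-injection frequencies differ sevenfold. This step assumes nothing about independence between injections.

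**Step 3, equal risk per injection.** With risk p per injection and independent injections, the chance of at least one reaction in k injections is 1 − (1 − p)^k:

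| p (assumed) | Weekly, k = 26 | Daily, k = 182 |
|---|---|---|
| 0.1% | 2.6% | 16.6% |
| 0.5% | 12.2% | 59.8% |
| 1% | 23.0% | 83.9% |

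Conversely, an equal percentage of children affected (anywhere from 10% to 40%) implies a per-injection risk 6.9 to 7.0 times higher on the weekly product.

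**Step 4, a worse weekly injection.** At p = 1% daily and 3% weekly, 1 − 0.97^26 = 54.7% of weekly children are affected, against 83.9% of daily children. Expected events per child are 26 × 0.03 = 0.78 against 182 × 0.01 = 1.82. The event rates meet only at 7%, since 26 × 0.07 = 1.82.

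**Step 5, departures from schedule.** The ratio of injections given is 7 × (daily adherence) / (weekly adherence). Assumed daily adherence of 71% to 100% (5/7 to 1) and weekly adherence of 90% to 100% give a range from 7 × (5/7) / 1 = 5.0 to 7 × 1 / 0.9 = 7.8. A weekly child above 50 kg has 52 injections in 26 weeks, so the ratio for that child is 182 / 52 = 3.5. The denominator should therefore be injections given, not doses scheduled.

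**The case against.** The strongest reply is that the plan asks a different question. A child receives a regimen, the phrase in section 5.2 can be read as comparing daily with weekly regimens, and no objective in section 4.1 asks for tolerability per injection. For regimen burden, per-child incidence is a valid measure. This stands: the per-injection figure is an addition, not a correction.

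A reader might infer that the planned output cannot reveal worse tolerability per injection, or that the weekly product would look better on every planned statistic. The documents do not support either reading. Event counts by arm are tabulated and schedules are fixed, so an approximate per-injection figure can be worked out. Listings show severity and relationship. Section 8.6.2 adds a dedicated reaction form, photographs and external dermatology review. The three weekly dose arms share one injection frequency during the first 52 weeks, so a dose-related signal among them is free of the 7:1 problem.

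A per-injection figure also has limits. Reactions are found mainly by inspection at visits, mostly 13 weeks apart, and are not linked to single injections. Under section 8.2 some weekly-arm visits fall on a planned dosing day, with blood sampling before the dose; if inspection also comes first, the last injection is nominally a week old. Daily children injected the evening before. Overlapping daily reactions may be recorded as one event, which would lower the daily figure. A reader might take events per injection as a clean measure of the product's tolerability; these features rule that out.

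The risks in steps 3 and 4 are assumptions, and clustering of reactions within particular children would shrink the contrast in percentages. Step 2 is unaffected. Finally, section 17 allows a separate, more detailed SAP, which might define the rate; the text reviewed does not.

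**Conclusion.** The point holds as a missing summary and an undefined denominator, not as missing data. Up to week 156 the planned statistics mix reaction frequency per injection with number of injections. On scheduled dosing, equal event counts in equal-sized arms correspond to a sevenfold difference per injection; the assumed adherence values move that factor between about 5.0 and 7.8, and split weekly doses would lower it. The conclusion that the summaries do not separate the two components does not depend on the assumed risks.

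Nothing here suggests that the weekly injection is in fact less well tolerated. That the rate is time-based is the likely reading but is not stated. The endpoint is supportive and untested, and with about 15 children in the daily arm any comparison stays descriptive. The change is worth making because section 5.2 relies on this comparison and the denominator is already collected.

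**What to change.** In section 17.4.2:

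1. State that the rate is events per patient-year of exposure.
2. For injection-site reactions, add events per 1,000 injections actually given. Take the denominator from the e-diary and count two injections where a weekly dose is split. Show it by arm and for the weekly arms combined, in the cumulative tables already planned up to weeks 26, 52, 104 and 156.
3. Label the per-child and per-year figures as regimen burden, and the per-injection figure as descriptive and supportive.
4. Footnote its limits: reactions are found mainly at visits whose timing relative to dosing differs by arm, overlapping daily reactions may be recorded as one event, and the daily arm has only about 15 children.

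The cost is a little extra tabulation, including a combined weekly column, with no new data collection. Section 3.1.6 describes the main period as completed, so the week-26 figure should be identified as added afterwards. The weekly product may look less favourable on this measure than on the per-child figures.

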8.4.2 Concomitant illness and medical history

A **concomitant illness** is any illness that is present at visit 1 or found as a result of a screening procedure.

Any change to a concomitant illness should be recorded during the trial. A clinically significant worsening of a concomitant illness must be reported as an AE according to section [12.2](#).

Medical history is a medical event that the subject has experienced in the past. At least history of GHD and other conditions that the investigator considers relevant to this trial must be recorded.

The following should be recorded in the eCRF:

- History of GHD:
 - Idiopathic or organic GHD
 - Diagnostic method (type of GH stimulation tests) and result of peak GH values (only if applicable)
 - Only required for cohort I and III: Standing height measured minimum 6 and maximum 18 months prior to screening. For cohort I this height measurement is used to assess inclusion criterion 6.
 - Parental height: standing height for both biological parents, either measured or reported (applies to visit 17)
- Concomitant illnesses
- Relevant medical history

The information collected for concomitant illness and medical history should include diagnosis, date of onset and date of resolution or continuation, as applicable.

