12.2 Reporting of adverse events

All events meeting the definition of an AE must be collected and reported. This includes events from the first trial-related activity at screening (visit 1) until the end of the post-treatment follow-up period. The events must be recorded in the applicable eCRF forms in a timely manner, see timelines below and [Figure 12-1](#).

During each contact with the trial site staff, the subject must be asked about AEs and technical complaints, for example by asking: "Have you experienced any problems since the last contact?"

All AEs, either observed by the investigator or subject, must be reported by the investigator and evaluated. Novo Nordisk assessment of expectedness is performed according to the following reference documents:

- NNC0195-0092 IB current version or any updates hereof [15](#).
- Norditropin® FlexPro® IB current version or any updates hereof [18](#).

All AEs must be recorded by the investigator on an AE form. The investigator should report the diagnosis, if available. If no diagnosis is available, the investigator should record each sign and symptom as individual AEs using separate AE forms.

For SAEs, a safety information form (SIF) must be completed in addition to the AE form. If several symptoms or diagnoses occur as part of the same clinical picture, one safety information form can be used to describe all the SAEs.

MESIs (medication errors) regardless of seriousness must be reported using both the AE form, the safety information form and a MESI form (medication error form). The MESI form is a form tailored to collect specific information related to the individual MESI.

The AE form for a non-serious AE not fulfilling the MESI criteria should be signed when the event is resolved or at the end of the trial.

Timelines for initial reporting of AEs:

The investigator must complete the following forms in the eCRF within the specified timelines:

- **SAEs:** The AE form **within 24 hours** and the safety information form **within 5 calendar days** of the investigator's first knowledge of the SAE.
Both forms must be signed within 7 calendar days from the date the information was entered in the eCRF.
- **SAEs fulfilling the MESI criteria (medication errors):** In addition to above, the MESI form (medication error form) **within 14 calendar days** of the investigator's first knowledge of the AE.

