12.3 Follow-up of adverse events

The investigator must record follow-up information by updating the forms in the eCRF.

Follow up information must be reported to Novo Nordisk according to the following:

- **SAEs:** All SAEs must be followed until the outcome of the event is “recovered/resolved”, “recovered/resolved with sequelae” or “fatal”, and until all queries have been resolved. Cases of chronic conditions, cancer or AEs ongoing at time of death (where death is due to another AE) may be closed with the outcome “recovering/resolving” or “not recovered/not resolved”. Cases can be closed with the outcome of “recovering/resolving” when the subject has completed the follow-up period and is expected by the investigator to recover. The SAE follow-up information should only include new (e.g. corrections or additional) information and must be reported **within 24 hours** of the investigator's first knowledge of the information. This is also the case for previously non-serious AEs which subsequently become SAEs.
- **Non-serious AEs:** Non-serious AEs must be followed until the outcome of the event is “recovering/resolving”, “recovered/resolved” or “recovered/resolved with sequelae” or until the end of the follow-up period stated in the protocol, whichever comes first, and until all queries related to these AEs have been resolved. Cases of chronic conditions, cancer or AEs ongoing at time of death (where death is due to another AE) may be closed with the outcome “recovering/resolving” or “not recovered/not resolved”. Cases can be closed with the outcome of “recovering/resolving” when the subject has completed the follow-up period and is expected by the investigator to recover.

- **Non-serious AE fulfilling the MESI criteria:** Non-serious AE fulfilling the MESI criteria must be followed as specified for non-serious AEs. Follow-up information on MESIs should only include new (e.g. corrections or additional) information and must be reported **within 14 calendar days** of the investigator's first knowledge of the information. This is also the case for previously reported non-serious AEs which subsequently fulfil the MESI criteria.

The investigator must ensure that the worst case severity and seriousness of an event is kept throughout the trial. A worsening of an unresolved AE must be reported as follow up with re-assessment of severity and/or seriousness of the event.

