17.3.2 Primary endpoint (cohort II and III)

The primary endpoint will be used to support the primary objective of evaluating safety of once-weekly NNC0195-0092 during up to 208 weeks of treatment in children with GHD:

- Incidence of adverse events, including injection site reactions

The primary endpoint will be analysed by cohort using descriptive statistics. All adverse events with onset after the first administration of trial product and up until end of trial visit or 14 days after last trial drug administration, whichever comes first, will be included in the analysis. Adverse events with onset 14 days or more after last trial drug administration will be reported in a separate listing.

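### AEs are classed by onset date alone while worsening is logged as follow-up, so an AE that first arises between visit 1 and first dose and worsens on trial drug is left out of the treatment-period counts

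*Combined protocol and SAP*

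**What the plan says.** **Collection.** Section 12.2 collects AEs well before dosing starts: "This includes events from the first trial-related activity at screening (visit 1) until the end of the post-treatment follow-up period". First dose is at visit 2. Tables 2-1 and 2-5 place visit 1 two to three weeks before that, and Section 8.3.2 caps the interval at 21 days.

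**Recording.** Section 12.3 states: "A worsening of an unresolved AE must be reported as follow up", with severity and seriousness re-assessed. It treats a change to serious as follow-up information due within 24 hours: "This is also the case for previously non-serious AEs which subsequently become SAEs". It adds: "The investigator must ensure that the worst case severity and seriousness of an event is kept throughout the trial".

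**Analysis, cohort I.** For the main period, Section 17.4.2 counts "All adverse events with onset after the first administration of trial product and up until week 26", or up to 14 days after last dose if that is sooner. The cumulative tables to weeks 52, 104, 156, 260 and 364 start from the same onset condition. For the remainder: "Adverse events with onset before first dosing will be reported in a separate listing".

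**Analysis, cohorts II and III.** Section 17.3.2 counts "All adverse events with onset after the first administration of trial product and up until end of trial visit", again with the 14-day limit. It mentions no pre-dose listing.

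**Concomitant illness.** Section 8.4.2 covers illness present at visit 1 or found by a screening procedure, and says: "A clinically significant worsening of a concomitant illness must be reported as an AE". Section 12.1 includes such worsening among AEs.

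**The concern.** Treatment-emergent status usually covers both new events and earlier events that get worse on treatment. Here the analysis rule has only the first half, and the recording rule does not supply the second by opening a new record. An event that begins in the screening interval and becomes severe or serious on trial drug then has no route into the incidence tables.

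AE incidence is the primary endpoint of cohorts II and III and a key secondary safety endpoint of cohort I. Cohorts II and III also admit children already on growth hormone, whose marketed product may stop as late as 12 hours before the first trial dose (Sections 5.1 and 8.2). An AE that starts in screening and worsens after that switch is one a safety reader would want in the tables.

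**Working it through.** The plan gives no figure to reproduce, so the main check is to apply the rules to one case and then to a near-identical one.

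**Case A.** A mild AE starts 7 days before first dose, after visit 1. It is not found by a screening procedure, is unresolved at dosing, and becomes serious in week 4.
1. Section 12.2: it is an AE record from its start in screening.
2. Section 12.3: the week 4 change is follow-up to that record, and the record now carries the worst severity and seriousness.
3. No section re-dates onset, so onset is taken to remain 7 days before dosing (an inference).
4. Section 17.4.2: it is excluded from the main-period counts, percentages and rates, and from every later cumulative table. It goes to the pre-dose listing, where it can read as a serious pre-treatment event.
5. Section 17.3.2: in cohorts II and III it is likewise excluded, with no listing named to hold it.

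**Case B.** The same illness is already present at visit 1. It is a concomitant illness, its week 4 worsening is itself an AE arising after first dose (Sections 8.4.2 and 12.1), and it is counted.

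The on-treatment course is the same in both cases. Only the start date relative to visit 1 differs.

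**Size.** From the documents: n = 60 in cohort I (Section 11.1), up to about 30 in cohorts II and III together (Section 6.1.2), and a screening interval of 14 to 21 days, midpoint 17.5. Assumed, because the documents give no values: r = 2 to 6 AEs per child-year, mean duration D = 7 to 30 days, and 5% to 15% of ongoing events worsening on drug.

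Expected AEs begun in screening and ongoing at first dose = n × (r/365) × D × (1 − exp(−17.5/D)). For n = 60:
- r = 2, D = 7: 2.30 × 0.918 = 2.1
- r = 4, D = 14: 9.21 × 0.713 = 6.6
- r = 6, D = 30: 29.59 × 0.442 = 13.1

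Multiplying by the worsening fraction gives 2.1 × 0.05 = 0.11 up to 13.1 × 0.15 = 1.96 events in cohort I. Half of that, 0.05 to 0.98, applies to n = 30. With the full 21 days the cohort I upper figure is 29.59 × (1 − exp(−0.7)) × 0.15 = 2.2. The formula does not remove events found by screening procedures, so it leans high.

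**In proportion.** Over four arms, 0.11 to 1.96 events is 0.03 to 0.49 per arm. At the same rates the main period would yield 60 × 2 × 0.5 = 60 to 60 × 6 × 0.5 = 180 events, so the omitted share is about 0.11/60 = 0.2% to 1.96/180 = 1.1%. One child is 1/15 = 6.7 points of an arm, or 1/30 = 3.3 points of cohorts II and III combined, but only in a row where that child has no other event. If events follow a Poisson process, the chance of having no AE at all by 26 weeks is exp(−1) = 37% at 2 per year and exp(−3) = 5% at 6 per year.

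**The case against.** **The key step is inferred.** Section 12.3 does not mention dates. AE-form instructions, or a separate SAP (optional under Section 17 and not among the documents), could settle the matter. This stands as a caveat. Follow-up to an existing record is most naturally read as keeping its onset, and nothing in the documents says otherwise.

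**The gap is narrow.** A reader might infer that anything starting between visits 1 and 2 is misfiled. The documents do not support that. Screening assessments may run throughout the interval (Section 8.1), whatever they find is a concomitant illness, and its worsening is an AE. Sections 8.6.6, 8.6.7 and 8.7 do the same for physical findings, vital signs and laboratory results. Eligibility is checked again at visit 2. A deterioration into a different diagnosis may also earn its own record, since Section 12.2 asks for the diagnosis. All of this stands and limits the point to the residual case.

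**The impact is easily overstated.** A reader might infer that drug harm is always understated, or that reported percentages move by 3 to 7 points. Neither follows. An illness may worsen naturally, so what is undercounted is events that worsened on treatment, not harm caused by treatment. Pre-dose onset does not depend on the randomised arm, so cohort I comparisons are not systematically biased unless worsening itself differs by treatment. The point shifts apply only where the child has no other event in the row; in an any-AE row the child is usually counted already.

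**The events are not hidden.** A cohort I event appears in a listing, a change to serious is reported within 24 hours, and the safety committee reviews safety throughout, with the data monitoring committee active to week 156. The AE analyses are descriptive and drive no decision rule. This also stands. The defect lies in the summary tables, not in safety surveillance.

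**Conclusion.** The gap is real but small. On the stated rules, an AE that first arises after visit 1 and before first dose, is not found by a screening procedure, is unresolved at dosing, and then worsens or becomes serious on trial drug is absent from all treatment-period counts. A like event already present at visit 1 is included, and nothing in the plan suggests that the difference is intended.

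The conclusion rests on the inference that the original onset date is kept. The size, about 0 to 2 events in cohort I and 0 to 1 in cohorts II and III, rests wholly on assumed AE rates, durations and worsening fractions. It matters mainly in individual preferred-term rows and in any summary by severity or seriousness, where one event is visible. It matters most for Section 17.3.2, because AE incidence is the primary endpoint there and no listing is provided for excluded events.

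**What to change.** - **Sections 17.3.2 and 17.4.2:** count an AE as treatment-emergent if its onset is after first administration, or if it began before first administration and increased in severity or became serious after it, within the windows already stated. Count each such event once.
- **Section 12.3 and the AE form:** capture the date of the increase in severity or seriousness on the existing record, so that the rule can be programmed. Do not also open a second record: doing both risks double counting and sits badly with the rule that one record keeps the worst severity and seriousness.
- **Cohort I data already collected:** the main period is complete (Section 3.1.6), so new form wording cannot change how those events were recorded. Apply the rule where follow-up entries or the eCRF audit trail (Section 13.1.1, which keeps old and new values with entry date and time) identify the change.

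The cost is analysis wording, one date field and a limited look-back. Event counts will rise slightly and may differ a little from tables already reported, which a footnote can explain.
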